9.1.1 Adverse Events

9.1.1.1 Monitoring

Subjects will be monitored at each study visit for adverse events. A specific enquiry will be made at the time of each check-in. The subjects will be queried with an open-ended question such as "How are you feeling?" or "How have you been feeling since your last visit?"

9.1.1.2 Serious Adverse Event

Any SAE will be reported to the Sponsor and the Institutional Review Board (IRB), as required. All SAEs will be reported to the Sponsor via fax or e-mail within one working day of becoming aware of the event, whether or not the serious events are deemed study treatment-related and within 5 working days to the IRB (24 hours of discovery if the event involves a death), as required.

An SAE is any AE or suspected adverse reaction that in the view of either the PI or Sponsor, results in any of the following outcomes: Death, a life-threatening adverse event, inpatient hospitalization or prolongation of existing hospitalization, a persistent or significant incapacity or substantial disruption of the ability to conduct normal life functions, or a congenital anomaly/birth defect. Important medical events that may not result in death, be life-threatening, or require hospitalization may be considered serious when, based upon appropriate medical judgment, they may jeopardize the subject and may require medical or surgical intervention to prevent one of the outcomes listed in the above definition.

Life-threatening is defined as an AE or suspected adverse reaction that in the view of the PI or Sponsor, its occurrence places the patient or subject at immediate risk of death. It does not include an adverse event or suspected adverse reaction that, had it occurred in a more severe form, might have caused death.

Treatment of SAEs will be performed by a physician, either at the site or at a nearby hospital emergency room. Where appropriate, medical test(s) and/or examination(s) will be performed to document resolution of event(s). Outcome may be classified as resolved, improved, unchanged, worse, fatal, or unknown (lost to follow-up).

If a SAE occurs to a subject on this study, contact the Sponsor's Representative listed in [Section 2](#).

10 DATA ANALYSIS

Data will be handled and processed according to Operating Procedures, which are based on the principles of GCP.

10.1 Statistical Methods

Detailed methodology for summary and statistical analyses of the data collected in this study will be documented in the Clinical Study Report.

10.1.1 Determination of Sample Size

This is an open-label study where subjects serve as their own control. The sample size was selected without statistical considerations.

10.1.2 Subjects to Analyze

Safety Population: All subjects who were administered at least one training session will be included in the safety evaluations.

Efficacy Population: All subjects who had at least one *leva* testing administration and measurement of any of the efficacy assessments post Screening Visit.

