4 STUDY EVENTS FLOW CHART

Study Procedures	Screen	Training Visits	Week 3	Week 6 Visit	End of Study/Early Termination
Visit →	1**	2-30	11	26	31
Inclusion/Exclusion Criteria	X				
Informed Consent	X				
Demographic data	X				
Medical History	X				
Height/Weight	X				
Urine Pregnancy Test	X				
Oral alcohol/Urine Drug Screen	X				
AE Monitoring		X	X	X	X
Concomitant Medication	X	X	X	X	X
Survey: MESA	X				
Surveys: UDI-6, IIQ-7, PGI-S, RUIS	X	X weekly	X	X	X
Surveys: FSFI, PISQ-IR (optional)	X				X
Patient's & Clinical Global Impression-Improvement			X	X	X
Voiding Diary	X		X		X
leva Training	X	X	X	X	
leva Testing/Angle Measurements	X	X* visits 6, 16 & 21	X*	X*	X*
Interview subject about experience using the device (optional)					X

*Preferably on Mondays

** Screening activities can be conducted over 1-2 visits

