9 STUDY PROCEDURES

The Study Events Flow Chart ([Section 4](#)) summarizes the procedures to be performed at each visit. Individual procedures are described in detail below. Additional evaluations/testing may be deemed necessary by the PI and/or the Sponsor for reasons related to subject safety.

Any nonscheduled procedures required for urgent evaluation of safety concerns take precedence over all routine scheduled procedures.

Screening visit:

This visit may be conducted in one to two visits, as needed. The study will be explained by the Study Director and the consent will be reviewed with prospective participants. The consent will be obtained by the licensed Physician Investigator or his Study Director. The study participation will be entirely voluntary.

Each subject will provide samples for drug screening, pregnancy testing, and buccal swabs for alcohol screening.

The following surveys will be administered:

- Medical, Epidemiologic and Social Aspects of Aging (MESA)
- Urinary Distress Inventory questionnaire, short version (UDI-6)
- Incontinence Impact Questionnaire, short form (IIQ-7)
- Patient Global Impression of Severity (PGI-S) Scale
- Revised Urinary Incontinence Scale (RUIS)
- Voiding diary – 24 hours intake and output and symptoms diary - to be taken home and completed within the first week of participation
- Female Sexual Function Index (FSFI) (optional)
- Pelvic Organ Prolapse/Incontinence Sexual Questionnaire (PISQ-IR) (optional)

Medical History will be obtained to include:

- Demographic data
- Height/weight
- Concomitant medication
- Latex allergy (for selection of disposable probe cover)

The female *leva* Trainer therapist will familiarize the subject with the *leva* Incontinence System™ and instruct on the technique of contraction.

The female *leva* Trainer will conduct baseline *leva* testing and measurements will include: Baseline angle; angle with Valsalva (or bear down maneuver); highest angle with pelvic floor muscles contraction; ability to sustain contraction and contractions in timed 15 seconds. This series is called the *leva* Test.

The subject will train for 2 ½ minutes using the *leva* device (*leva* Training) – each cycle will have 15 seconds of contraction with 15 seconds of relaxation. Participants will perform 5 alternating repetitions.

The female *leva* Trainer will record *leva* device measurements.

Study visits 2-30 (with the female leva Trainer):

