Frequency: once a day 5 days a week. The female leva Trainer will supervise the participants on performing 2 1/2 minutes of 5 repetitions of pelvic floor exercises using the leva Incontinence System TM (leva Training)

Once a week, preferably Mondays, during the about 6-8 week study period:

The subjects will be asked to perform a series of 5 exercises “leva Test” to test the effect of the daily training and follow the test with the 2 ½ minutes of training (leva Training). The female leva Trainer will record leva device measurements.

The study participants will be given the following surveys:

- UDI-6
- IIQ-7
- PGI-S
- RUIS

At 3 weeks:

The subjects will be asked to perform a series of 5 exercises (leva Test) to test the effect of the daily training and follow the test with the 2 ½ minutes of training (leva Training). The female leva Trainer will record leva device measurements.

The study participants will be given the following questionnaires:

- UDI-6
- IIQ-7
- PGI-S
- PGI-I
- RUIS
- Voiding diary completion

The Study Director or PI will complete the Clinician’s Global Impression of Improvement (CGI-I) evaluation.

At 6 weeks:

The subjects will be asked to perform a series of 5 exercises (leva Test) to test the effect of the daily training and follow the test with the 2 ½ minutes of training (leva Training). The female leva Trainer will record leva device measurements.

The study participants will be given the following questionnaires:

- UDI-6
- IIQ-7
- PGI-S
- PGI-I
- RUIS

The Study Director or PI will complete the Clinician’s Global Impression of Improvement

(CGI-I) evaluation.

At the End of Study/ Early Termination visit:

The subjects will be asked to perform a series of 5 exercises (*leva* Test) to test the effect of the daily training. The female *leva* Trainer will record *leva* device measurements.

The study participants will be given the following questionnaires:

- UDI-6
- IIQ-7
- PGI-S
- PGI-I
- RUIS
- Voiding diary completion
- FSFI (optional)
- PISQ-IR (optional)

The Study Director or PI will complete the Clinician's Global Impression of Improvement (CGI-I) evaluation.

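### No adverse-event monitoring is charted at Screening, where the device is first used, and the Safety Population leaves out a woman exposed only to the baseline leva Test

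*Combined protocol and SAP*

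**What the plan says.** Section 10.1.2 defines the Safety Population in one sentence: "All subjects who were administered at least one training session will be included in the safety evaluations". The Efficacy Population, defined next to it, refers instead to leva testing.

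The flow chart in section 4 has five columns: Screen, Training Visits, Week 3, Week 6, and End of Study/Early Termination. The row "AE Monitoring" is blank under Screen and marked in the other four. The row below it, "Concomitant Medication", is marked in all five. The row "leva Testing/Angle Measurements" is marked under Screen, and so is leva Training.

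Section 9 says that the chart "summarizes the procedures to be performed at each visit" and that details follow in the text. Its Screening visit text describes a baseline leva Test, whose measurements include "ability to sustain contraction and contractions in timed 15 seconds". It then describes a leva Training session in which "each cycle will have 15 seconds of contraction with 15 seconds of relaxation".

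Section 9.1.1.1 requires adverse-event monitoring at every study visit, with a specific enquiry at check-in. Section 10.2 says that monitoring runs throughout the study and that safety data are listed by subject. The synopsis describes Screening as one or two study visits. Exclusion 17 in section 8.3.2 bars women who cannot tolerate the device.

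**The concern.** Leaving adverse-event collection out of a screening visit is normal when screening comes before exposure. Here Screening includes the first exposure, to both the Test and the training. The one column without monitoring is therefore the one in which a woman first has the device inserted.

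The population rule adds a second, separate gap. It counts training sessions, not use of the device, so a woman who has the Test and goes no further has been exposed but does not qualify. Reported adverse events and serious adverse events are the only Safety and Tolerability endpoint in section 7.2. Women who stop at the Test may include those who tolerate the device least, so a non-serious event left out in this way would tend to favour the device.

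**Working it through.** The plan gives no figure to reproduce on this point. The check sets the sections side by side.

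**Step 1. Marks in the flow chart, out of five columns**

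| Row | Marked | Blank |
|---|---|---|
| Adverse-event monitoring | 4 | Screen |
| Concomitant medication | 5 | none |
| leva Training | 4 | End of Study/Early Termination |
| leva Testing | 5 (under Training Visits, only visits 6, 16 and 21) | none |

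Device use of either kind is marked in 5 of 5 columns and monitoring in 4 of 5. The difference, 5 − 4 = 1, is Screen. Because the adjacent medication row keeps its Screen mark, the blank does not look like a column lost in extraction.

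**Step 2. Chart against text.** Section 9.1.1.1 covers every study visit, and the synopsis counts Screening among the study visits. On those two statements, monitoring is due at Screening and the chart omits it. Section 10.2 points the same way but more weakly, because it does not say when the study begins.

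**Step 3. Is the Test a training session?** Four places say that it is not.

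- Section 8.1 describes a training session as 2.5 minutes of alternating 15-second contraction and rest.
- Section 9 names the Test as its own series, which includes a bearing-down angle.
- At the weekly, Week 3 and Week 6 visits the Test is followed by training. At End of Study the instruction reads "to test the effect of the daily training. The female" and goes straight to the recording of measurements, with no training. The chart agrees: End of Study is the one column with testing and no training.
- Within section 10.1.2, one population refers to training and the other to testing.

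A woman with the baseline Test only has 0 training sessions and does not meet the rule.

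**Step 4. Can this happen?** The Screening text describes the Test before the training. That order is explicit only for later visits and is inferred here. Screening may also be split over two visits, so the Test and the first training could fall on different days. A woman who finds the device intolerable during the Test meets exclusion 17 and must not be enrolled. Consent is obtained before Screening (section 11.1.3), so she is consented and exposed.

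**Step 5. Where would her event be recorded?** The check-in enquiry at Screening precedes device use. A woman who returns can be asked at Visit 2 how she has felt since the last visit. A screen failure may have neither a Visit 2 nor an Early Termination visit. Serious events are still reported under section 9.1.1.2, whatever the population.

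**Step 6. How many women?** The documents do not say. The ceiling of 25 counts women who met the criteria at Screening, so it does not bound the number who fail there.

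**The case against.** The strongest reply is that a woman who cannot tolerate the device at the first Test is a screen failure on the protocol's own terms. Defining the Safety Population by receipt of the study treatment, which section 8.4.1 describes as training, is a recognisable choice. This stands in part: including her is partly a matter of preference, and the fix should say openly that it brings in some screen failures. But the insertion was a study procedure done after consent, and the safety endpoint concerns events with the device, so the choice should be stated and not left to follow from one word.

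A second reply is that the blank cell has an innocent explanation. At check-in for Screening there is no exposure to ask about, and section 9 gives Screening a heading apart from visits 2 to 30. That makes the conflict less stark, but the synopsis wording still places Screening among the study visits. The timing point also shows that a chart mark alone would not capture events after first use.

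A reader might infer more: that the protocol has no adverse-event rule for Screening, that Screening events are bound to be lost, or that the safety results are biased. The documents do not support this. Section 9 calls the chart a summary, and section 9.1.1.1 supplies a general rule. Women who return can report at Visit 2. If a woman is instead handled as a withdrawal under section 8.3.3, her reason is reported and an Early Termination visit with monitoring could apply, although she still would not meet the population rule. Serious-event reporting and the by-subject listing in section 10.2 are not limited to the Safety Population, and no safety rate is planned that could be biased.

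**Conclusion.** Both parts hold, and the point is minor.

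The mismatch between the flow chart and section 9.1.1.1 stands whether or not any woman has the Test alone. It rests on the synopsis counting Screening as a study visit; section 10.2 is only supporting evidence.

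The population gap follows from the literal wording of section 10.1.2 and the protocol's consistent separation of Test from training. Its practical size depends on how many consented women are exposed to the baseline Test and never train. That number is not given and may be zero. For a screen failure the two gaps can combine: no enquiry is charted at what may be her only visit, and she is then outside the population.

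Because safety data are listed and not estimated, the most that can be lost is a non-serious event missing from the record or from a listing restricted to the Safety Population.

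**What to change.** 1. Reconcile section 4 with section 9.1.1.1. Mark adverse-event monitoring under Screen, and state that at Screening the enquiry is made after the leva Test and training, not only at check-in.
2. Redefine the Safety Population in section 10.1.2 as all consented subjects in whom the leva device was used at least once, for Test or training. State that this includes women who then fail screening because they cannot tolerate the device.

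The cost is one chart mark with a short note in section 9.1.1.1, one reworded sentence in section 10.1.2, and a brief enquiry at the end of Screening. The downside is that a few screen failures may enter the safety listing, which may then look slightly less favourable.

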10.2 Safety Evaluation

Safety data will be populated in individual CRFs. All safety data will be listed by subject.

AEs and SAEs will be monitored throughout the study. All SAEs will be recorded and reported. Concomitant medications and medical history will be listed by subject.

11 STUDY ADMINISTRATION

11.1 Ethics

11.1.1 Institutional Review Board

This protocol will be reviewed by Chesapeake Research Review, Inc., an IRB and the study will not start until the IRB has approved the protocol or a modification thereof. The IRB is constituted and operates in accordance with the principles and requirements described in the US Code of Federal Regulations (21 CFR Part 56). The IRB is compliant to International Conference on Harmonisation (ICH) guidelines, and may be reached at:

Chesapeake IRB
[name]
[name]
[contact]

11.1.2 Ethical Conduct of the Study

This research will be carried out in accordance with the protocol, US Code of Federal Regulations, GCP, 21 CFR Parts 50 and 56, the ethical principles set forth in the Declaration of Helsinki, and the ICH harmonized tripartite guideline regarding GCP (E6 Consolidated Guidance, April 1996).

11.1.3 Subject Information and Consent

The purpose of the study, the procedures to be carried out and the potential hazards will be described to the subjects in non-technical terms. Subjects will be required to read, sign and date an ICF summarizing the discussion prior to Screening, and will be assured that they may withdraw from the study at any time without jeopardizing their medical care.

Subjects will be given a copy of their ICF.

11.2 Termination of the Study

The Principal Investigator reserves the right to terminate the study in the interest of subject welfare. The Sponsor may terminate the study for administrative reasons.

11.3 Data Quality Assurance

The Principal Investigator will designate personnel responsible for implementing and maintaining quality assurance and quality control systems to ensure that the study is conducted, and that data are generated, documented and reported in compliance with the study protocol, GCP and Good Laboratory Practice requirements as well as applicable regulatory requirements and local laws, rules and regulations relating to the conduct of the clinical study.

11.4 Direct Access to Source Data/Documents

The Principal Investigator will ensure that the Sponsor, IRB and domestic and foreign regulatory authorities will have direct access to all study sites, source data/documents, and

reports for the purpose of monitoring and auditing. In the event that other study-related monitoring should be done by other parties, those parties will be required to sign a confidentiality agreement prior to any monitoring or auditing.

11.5 Study Device Supplies, Packaging and Labeling

The Sponsor will supply sufficient quantities of devices to allow completion of this study. Each subject will be provided with her own device and can retain the device at the end of the study. The device has a value of about \$700. If the subject does not already own an iPhone to run the *leva* software they will be provided at no charge an iPOD touch (\$250 value) to use. It will be up to the discretion of the Sponsor if the iPOD touch needs to be returned to the study site or can be retained by the subject at the end of the study. Records will be made of the receipt and dispensing of devices supplied. This accountability record will be available for inspection at any time. At the completion of the study, the original accountability record will be available for review by the Sponsor upon request.

11.6 Data Handling and Record Keeping

All raw data generated in connection with this study, together with the final report, will be retained for at least 5 years after completion of the final report. These documents should be retained for a longer period however if required by the applicable regulatory requirements or by an agreement with the Sponsor. It is the responsibility of the Sponsor to inform the PI/Institution as to when these documents no longer need to be retained.

11.7 Publication Policy

All unpublished information given to the Principal Investigator by the Sponsor shall not be published or disclosed to a third party without the prior written consent of the Sponsor.

The data generated by this study are considered confidential information and the property of the Sponsor. This confidential information may be published only in collaboration with participating personnel from the Sponsor or upon Sponsor's written consent to publish the article.

